9.4.3 Analysis of Safety

Safety analyses will be conducted on the SAF.

9.4.3.1 Adverse Events

AEs will be coded using MedDRA and graded using NCI-CTCAE v5.0.

A treatment-emergent adverse event (TEAE) is defined as an AE observed after starting administration of the IP until 30 days after the final administration of IP. An IP-related TEAE is defined as any TEAE with a causal relationship assessed as “yes” by the investigator.

The number and percentage of participants with TEAEs, drug-related TEAEs, serious TEAEs, drug-related serious TEASs, TEAEs leading to withdrawal of treatment and drug-related TEAEs leading to withdrawal of treatment will be summarized by SOC, preferred term and treatment group. The number and percentage of TEAEs by severity will also be summarized. The worst severity will be summarized if the same AE is recorded more than once for a participant.

AE data will be listed.

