- Grade 3 LFT elevations that resolve to \leq grade 1 within 7 days; LFT elevations lasting > 7 days that are considered to be clinically significant and at least possibly related to ASP0739 and/or pembrolizumab will be considered to be a DLT
- Grade 3 or lower irAEs that resolve to \leq grade 1 within 72 hours of onset after starting treatment including corticosteroids

Participants who are tolerating ASP0739 and/or pembrolizumab at a dose level that is being reviewed due to the occurrence of DLTs in another participant will not be automatically precluded from continued dosing during the safety review, and will be allowed to continue dosing for as long as tolerated unless directed otherwise as a result of the safety review by the DESC.

Dose escalation within individual participants will not be allowed. Refer to the *Participant Replacement during Dose Escalation/Safety Lead-in* section for definition of evaluable participants.

DLTs Requiring Discontinuation of Treatment

- If a study participant develops a grade 4 DLT after receiving cycle 1, then the study participant should be discontinued from treatment.
- If a study participant develops a grade ≥ 3 non-hematological AE that does not resolve to \leq grade 2 within 72 hours of onset, it should be considered a DLT and the study participant should be discontinued from treatment.
- If there is a delay in administration of the second cycle by > 4 weeks, it would result in discontinuation from treatment after discussion with the sponsor.

Study Enrollment Interruption:

Study enrollment will be temporarily interrupted pending review of the following:

- Any death that is not related to disease progression occurring within 30 days of receiving ASP0739 and/or pembrolizumab
- Occurrence of 2 grade ≥ 4 DLTs in 2 study participants
- Any grade 4 hypersensitivity reaction/anaphylaxis

Participant Replacement during Dose Escalation/Safety Lead-in:

Participants may be replaced in the safety lead-in or dose escalation cohort if:

- Participant is discovered to have enrolled without fully satisfying eligibility criteria.
- Participant did not receive the planned dose in cycle 1 for reasons other than DLT.
- Participant has no DLT and withdraws from the study before the end of the DLT evaluation period.

The decision to replace participants will be made by the sponsor based on the above criteria.

Recommended Phase 2 Dose

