6.1.1 Investigational Product Administration

ASP0739 will be diluted with Lactated Ringer's injection to approximately 50 mL and administered by intravenous infusion at 4 to 6 mL/min infusion rate through a dedicated intravenous line every 28 days during treatment beginning on C1D1.

Pembrolizumab will be administered at a dose of 400 mg via 30-min intravenous infusion every 6 weeks beginning on C1D1. Sites should make every effort to target infusion timing to be as close to 30 min as possible. However, given the variability of infusion pumps from site to site, a window between -5 min and +10 min is permitted (i.e., infusion time is 30 min (-5 min/+10 min)). The pembrolizumab infusion should be completed at least 1 hour prior to the ASP0739 injection for participants in the ASP0739 and pembrolizumab combination therapy arms.

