9.5 Interim Analysis

Safety, pharmacokinetic and other clinical data will be reviewed on an ongoing basis to determine if the study will proceed to the next dose level/phase.

For phase 2, according to the BOP2 design, the futility analysis for efficacy will be performed at the end of stage 1. If the response rate does not meet the optimal stopping boundaries, then stage 2 will be opened.

The safety in phase 2 will be monitored using a Bayesian logistic model based on all DLT data obtained at the time of the analysis for both escalation and expansion cohorts and drug-related TEAEs leading to death. Safety monitoring with these models will start when phase 2 is opened. Enrollment in phase 2 may be held based on the following 2 criteria:

1. If the posterior mean of the safety event rate is higher than 30% as indicated by Bayesian logistic model across all tumor types at a given dose level for monotherapy or combination therapy, then enrollment may be held in all expansion cohorts at that dose level and at higher dose levels for that therapy.
2. Additionally, if the posterior mean of the safety event rate is higher than 30% as indicated by Bayesian logistic model in a specific tumor type at a dose level for monotherapy or combination therapy, enrollment of that dose level and any higher dose level may be held for that tumor type and that therapy.

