10.10 Appendix 10: Dose Modification and Toxicity Management for Immune-related Adverse Events

AEs associated with pembrolizumab exposure may represent an immune-related response. These irAEs may occur shortly after the first dose or several months after the last dose of pembrolizumab treatment and may affect more than one body system simultaneously. Therefore, early recognition and initiation of treatment is critical to reduce complications. Based on existing clinical study data, most irAEs were reversible and could be managed with interruptions of pembrolizumab, administration of corticosteroids and/or other supportive care. For suspected irAEs, ensure adequate evaluation to confirm etiology or exclude other causes. Additional procedures or tests such as bronchoscopy, endoscopy, skin biopsy may be included as part of the evaluation. Dose modification and toxicity management guidelines for irAEs associated with pembrolizumab are provided in [Table 16](#).

Based on the mechanism of action of ASP0739, immune-related adverse reactions (e.g., fever, headache, fatigue, hot flashes, diarrhea and muscular and joint pain) should be considered (see Section [2.3.1](#)) and managed as required per SOC. In case of such events, ensure adequate evaluation to confirm etiology or exclude other causes. In addition, the study medical monitor should be contacted to discuss event monitoring, follow up and study treatment management.

Table 16 Dose Modification and Toxicity Management Guidelines for Immune-related Adverse Events Associated with Pembrolizumab

General instructions:

1. Severe and life-threatening irAEs should be treated with intravenous corticosteroids followed by oral steroids. Other immunosuppressive treatment should begin if the irAEs are not controlled by corticosteroids.
2. Pembrolizumab must be permanently discontinued if the irAE does not resolve or the corticosteroid dose is not ≤ 10 mg/day within 12 weeks of the last pembrolizumab treatment.
3. The corticosteroid taper should begin when the irAE is \leq grade 1 and continue at least 4 weeks.
4. If pembrolizumab has been withheld, pembrolizumab may resume after the irAE decreased to \leq grade 1 after corticosteroid taper.

Table continued on next page

irAEs	Toxicity grade (CTCAE v5.0)	Action with pembrolizumab	Corticosteroid and/or other therapies	Monitoring and follow-up

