### **5.2.3 Safety Endpoint: Adverse Events (AEs)**

An AE is any untoward medical occurrence in a participant or clinical study participant, temporally associated with the use of study IP and other study treatments, whether or not considered related to the study IP and other study treatments.

A treatment-emergent adverse event (TEAE) is defined as an AE observed after starting administration of the IP until 30 days after the final administration of IP. An IP-related TEAE is defined as any TEAE with a causal relationship assessed as “yes” by the investigator or with missing assessment of the causal relationship.

If the adverse event occurs on Day 1 and the onset check box is marked “Onset after first dose of study IP” or the onset check box is left blank, then the adverse event will be considered treatment emergent. If the adverse event occurs on Day 1 and the onset check box is marked “Onset before first dose of study IP”, then the adverse event will not be considered treatment emergent. If a participant experiences an event both during the pre-investigational period and during the investigational period, the event will be considered as TEAE only if it has worsened in severity (i.e. it is reported with a new start date). All adverse events

collected that begin within 30 days after taking the last dose of study IP will also be counted as TEAE.

The number and percentage of participants with TEAEs, IP-related TEAEs, serious TEAEs, IP-related serious TEASs, TEAEs leading to withdrawal of treatment and IP-related TEAEs leading to withdrawal of treatment will be summarized by SOC, preferred term and treatment group. The number and percentage of TEAEs by severity will also be summarized. The worst severity will be summarized if the same AE is recorded more than once for a participant.

AE data will be listed.

Immune-related AE (irAE) and infusion related reactions (IRR) will be considered as Adverse Events of Special Interest (AEsi). The list of events classified as AEsi may change during the study due to ongoing pharmacovigilance.

Time to first onset of irAE will follow the following algorithm:

Situation	Date of Event or Censor	Outcome
AE of interest observed	Date of first onset	Event
No AE of interest observed and treatment ongoing	Date of data cutoff	Censor
No AE of interest observed and treatment discontinued	Date of last dose + 30 days	Censor

Time to First Onset = Date of Event or Censor – Date of First Dose +1

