### **6.5.2 Adverse Events**

For the purpose of safety assessments in this study, events recorded during the pre-investigational period will be classified as Baseline Signs and Symptoms. All AEs recorded on treatment including within 30 days from the last study treatment and SAEs on treatment including within 90 days of the last study treatment will be summarized.

Summaries and listings of SAEs and Serious TEAEs include SAEs upgraded by the sponsor based on review of the Sponsor's list of Always Serious terms if any upgrade was done.

The coding dictionary for this study will be Medical Dictionary for Regulatory Activities (MedDRA). It will be used to summarize AEs by SOC and PT. AEs will be graded using National Cancer Institute's Common Terminology Criteria for AEs (NCI-CTCAE).

An overview table will include the following details by dose level, phase, and overall:

- Number and percentage of participants with TEAEs
- Number and percentage of participants with IP-related TEAEs
- Number and percentage of participants with TEAE leading to death
- Number and percentage of participants with IP-related TEAE leading to death
- Number and percentage of participants with serious TEAEs and Astellas upgraded serious TEAE
- Number and percentage of participants with serious IP-related TEAEs and Astellas upgraded serious IP-related TEAE
- Number and percentage of participants with TEAEs leading to permanent discontinuation of study IP
- Number and percentage of participants with IP-related TEAEs leading to permanent discontinuation of study IP
- Number and percentage of deaths

The number and percentage of participants with TEAEs, as classified by SOC and PT will be summarized by dose level, phase, and overall. Summaries will be provided for:

- DLTs within the DLT observation period
- All DLTs
- TEAEs
- IP-related TEAEs
- Serious TEAEs and Astellas upgraded serious TEAE
- IP-related serious TEAEs and IP-related Astellas upgraded serious TEAE
- TEAEs leading to permanent discontinuation of study IP
- IP-related TEAEs leading to permanent discontinuation of study IP
- TEAEs excluding serious adverse events that equal to or exceed a threshold of 10% in any dose level
- Common TEAEs that equal to or exceed a threshold of 10% in any dose level
- TEAEs leading to death
- IP-related TEAE leading to death
- CTCAE Grade 3 or higher TEAEs
- IP-related CTCAE Grade 3 or higher TEAEs

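### Once pembrolizumab is given alone, its 42-day interval exceeds the 30-day TEAE window, so late-interval events that end treatment are not counted; separately, the SAP promises SAEs to 90 days but lists only 30-day tables

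*Protocol*

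**What the plan says.** **TEAE window.** Protocol 9.4.3.1 counts "an AE observed after starting administration of the IP until 30 days after the final administration of IP". SAP 5.2.3 uses the same 30 days but dates by start: events "collected that begin within 30 days after taking the last dose of study IP will also be counted as TEAE". SAP 5.2.3 also censors time to first immune-related event at last dose plus 30 days once treatment has been discontinued.

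**Dosing.** Both products are investigational product (protocol 6.1). Protocol 6.1.1 states: "Pembrolizumab will be administered at a dose of 400 mg via 30-min intravenous infusion every 6 weeks beginning on C1D1". ASP0739 is given "through a dedicated intravenous line every 28 days during treatment". In protocol Tables 1 and 2, pembrolizumab doses 5 to 17 are given alone, with visits every 6 weeks (±3 days).

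**Late events.** Protocol Appendix 10 says immune-related events may appear "several months after the last dose of pembrolizumab treatment". Protocol Table 3 schedules AE and SAE assessment at 30, 60 and 90 days after the last dose.

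**Rules that use the window.** The phase 2 safety model in protocol 9.5 takes DLTs and "drug-related TEAEs leading to death". The enrollment-interruption rule in protocol 4.1 uses "Any death that is not related to disease progression occurring within 30 days of receiving ASP0739 and/or pembrolizumab".

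**SAP summaries.** SAP 6.5.2 says "SAEs on treatment including within 90 days of the last study treatment will be summarized". The serious-event tables it then lists are all of serious TEAEs.

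**The concern.** A TEAE window should span at least one dosing interval. If it does not, whether a late-interval event counts depends on what happens next. Suppose a laboratory abnormality is first dated to the predose visit on day 42. If the dose is given, the final administration moves forward and the event is a TEAE. If the event stops treatment, the final administration stays 42 days back and the event is not one. The definition then tends to remove treatment-ending events from the table meant to count them.

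Safety is a primary endpoint, and immune-related events are the events of special interest. The same limit reaches the Section 9.5 model, where fatal TEAEs are the only input besides DLTs. DLTs run 28 days from C1D1 and cannot pick up a late event.

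The SAP raises a second, independent problem. Its text commits to a 90-day SAE summary, but no table in its list would deliver one.

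**Working it through.** **Inputs.** TEAE window: 30 days (protocol 9.4.3.1, SAP 5.2.3). Pembrolizumab: every 6 weeks, 17 doses, 96 weeks (protocol 6.1.1; Table 2 footnote d). ASP0739: every 28 days, up to 6 doses. Visit window in the pembrolizumab-alone phase: ±3 days. End-of-treatment visit: within 7 days.

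**Step 1: reproduce the schedule.** (17 − 1) × 6 = 96 weeks, as stated. Dose 3 falls at (3 − 1) × 6 = week 12 and dose 5 at (5 − 1) × 6 = week 24, matching the pulmonary-function footnote to Table 2.

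**Step 2: find the gaps between administrations of any product.** Pembrolizumab falls on days 1, 43, 85, 127, 169 and so on; ASP0739 on days 1, 29, 57, 85, 113 and 141. With all six ASP0739 doses, the gaps up to pembrolizumab dose 5 (day 169) are 28, 14, 14, 28, 28, 14, 14 and 28 days. On this nominal schedule none exceeds 30. After dose 5, all 12 gaps are 42 days. If ASP0739 stops sooner, the long gaps start sooner:

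| ASP0739 doses given | First gap over 30 days starts | Gaps over 30 days |
|---|---|---|
| 6 | day 169 | 12 |
| 4 | day 85 | 14 |
| 2 | day 43 | 15 |
| 1 | day 1 | 16 |

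**Step 3: size the uncovered period.** 42 − 30 = 12 days, and 12/42 = 28.6%. With the visit window: 39 − 30 = 9 days (9/39 = 23.1%) to 45 − 30 = 15 days (15/45 = 33.3%). When another dose follows, the final administration moves forward and nothing is lost. Only a participant's last interval is exposed.

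**Step 4: locate the stopping visit.** If treatment is stopped at the day-42 visit, the 30-day safety visit has already passed (30 + 3 = day 33). The end-of-treatment visit falls by day 42 + 7 = 49, or 45 + 7 = 52 with the window. Both lie inside the 90 days over which AEs are collected.

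**Step 5: compare the SAP with itself.** SAP 6.5.2 commits to SAEs within 90 days. Its overview and its tables by system organ class and preferred term then show serious TEAEs, with sponsor-upgraded terms, which SAP 5.2.3 limits to 30 days. An SAE starting on days 31 to 90 therefore falls within the commitment but in no listed serious-event table. This holds for single-agent participants too.

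**Not computable.** The effect on the 30% posterior-mean threshold in protocol 9.5 cannot be calculated, because the documents give no prior for the logistic model.

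**The case against.** The case against a broad reading is strong, and most of it stands.

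- **No effect on the pembrolizumab data.** SAP Section 1 records that no combination treatment was given. ASP0739 alone has a nominal 28-day interval, inside the 30-day window. This stands.
- **Detection is not onset.** A reader might infer that any event found at the next visit drops out. SAP 5.2.3 dates by start, so an event found on day 42 that began by day 30 is a TEAE. Symptomatic immune-related events carry their own onset dates. The exposed events are those that begin on days 31 to 42, including laboratory findings first dated to the visit. The protocol's verb is *observed* and the SAP's is *begin*, and the two are not equivalent.
- **Late events are not lost.** A reader might infer that they vanish. AEs are listed. Shift tables use the worst post-baseline grade, and the liver table uses the highest value in the investigational period (SAP 6.5.4, 6.5.4.1). SAP 6.5.3 summarizes special-interest events without a TEAE limit in its text, and the overview in 6.5.2 counts deaths.
- **Oversight is wider than the two rules.** The DESC reviews aggregate phase 2 safety data and all available findings. A fatal event that begins by day 30 remains a TEAE leading to death even if death comes later.
- **A blanket 90-day TEAE definition is debatable.** It would extend the window for single-agent cohorts that have no interval gap, and it would admit more disease-related events.

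What survives is narrower. Listings and laboratory tables do not replace incidence tables of events leading to withdrawal, and they do not feed the Section 9.5 model. One could argue that SAP 6.5.2 treats SAEs as distinct from serious TEAEs and that its table list is merely incomplete; even so, the promised table has to be added.

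**Conclusion.** The point holds in limited form, in two parts.

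1. **Protocol plan.** When pembrolizumab is given without ASP0739, 12 of the 42 days in a participant's last interval (9 to 15 days with the visit window) lie outside the TEAE window. Events with onset there that end treatment leave the TEAE, serious TEAE and withdrawal tables, and a fatal drug-related one is not counted in the Section 9.5 model. This rests on the nominal schedule and on dating by onset. The percentage is calendar time; the documents give no event rate from which to estimate how many events are affected.
2. **SAP.** The 90-day SAE commitment in 6.5.2 has no matching table. This affects the single-agent analysis actually run.

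The documents do not support reading the first part as a bias in reported results, because no participant received the combination. Nor do they support it for the period when ASP0739 is also given every 28 days.

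**What to change.** - **Keep the 30-day TEAE tables.** Add tables of SAEs, immune-related events and AEs leading to withdrawal with onset up to 90 days after the last investigational product, or up to the start of new anticancer therapy if earlier.
- **Pembrolizumab participants.** Count as treatment-emergent at least all onsets within the 42-day interval plus the visit window (42 + 3 = 45 days). Use the same window for the drug-related fatal-event input to protocol 9.5.
- **SAP 6.5.2.** Add the SAE table that its 90-day sentence promises.
- **Wording.** Reconcile *observed* in protocol 9.4.3.1 with *begin* in SAP 5.2.3.
- **Interruption rule.** The 30-day death criterion in protocol 4.1 and the statement on late immune-related events in Appendix 10 must be reconciled. No replacement rule is proposed here.

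**Cost.** Text changes and a programming flag, with no new data. The later window will take in some disease-related events. Capture to 90 days will not be uniform, because safety follow-up visits may be brought forward ahead of new anticancer therapy; the added tables should carry that note.

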9.4.3.2 Laboratory Assessments

For quantitative clinical laboratory measurements (hematology and biochemistry), descriptive statistics will be used to summarize results and change from baseline by single agent and combination therapy arms, by dose level, and overall and by time point. Shifts from baseline to the worst grade based on NCI-CTCAE v5.0 in laboratory tests will also be tabulated.

Laboratory data will be listed.

9.4.3.3 Vital Signs

Descriptive statistics will be used to summarize vital sign results and changes from baseline for participants in the SAF by single agent and combination therapy arms, by dose level and time point.

Vital signs data will be listed.

9.4.3.4 Electrocardiogram

9.4.3.4.1 Routine 12-lead Electrocardiogram

The routine 12-lead ECG results will be summarized by single agent and combination therapy arms, by dose level and by time point.

Interpretations of routine 12-lead ECG results will be summarized by single agent and combination therapy arms, by dose level and by time point.

12-lead ECG data interpretations and quantitative values will be listed.

9.4.3.5 Eastern Cooperative Oncology Group Performance Status

Summary statistics (number and percent of participants) for each category of the ECOG performance status at each assessment will be provided. The change from baseline to final visit or early termination will also be summarized. Negative change scores indicate an improvement. Positive scores indicate a decline in performance.

9.4.3.6 Concentration-response Relationship Analysis

Exploratory analysis between pharmacokinetic parameter and clinical measures (e.g., efficacy or safety) may be performed.

9.4.4 Analysis of Pharmacokinetics

Cellular DNA load and kinetic parameters for ASP0739 pharmacokinetics will be summarized by using descriptive statistics including n, mean, standard deviation, minimum, median, maximum, coefficient of variation (CV), geometric mean, and geometric CV.

Time-course of cellular DNA load will be plotted as appropriate. Participants with sufficient cellular DNA samples will have kinetic parameter estimates for ASP0739 including calculation of AUC (including AUC_{last} , AUC_{28d} , AUC_{inf} , C_{max} , C_{trough} and t_{max}) using standard noncompartmental analysis. For pharmacokinetic parameter, t_{max} , only n, median, minimum and maximum will be calculated.

Descriptive statistics of pembrolizumab pharmacokinetics may be tabulated.

